12.2.2.2 Treatment-emergent Adverse Events Related to Study Drug

Drug-related TEAEs reported by $\geq 5\%$ of subjects in the udenafil group ([Table 14.3.7A](#)) included headache (38.0%), flushing (14.5%), epistaxis (7.5%), dizziness (6.5%), nausea (6.5%), erection increased (6.3% of males), and spontaneous penile erection (6.3% of males). Drug-related TEAEs reported by $\geq 5\%$ of subjects in the placebo group included headache (22.0%), dizziness (7.0%), and flushing (6.0%). A notably greater percentage (≥ 5 percentage points) of subjects in the udenafil group as compared to the placebo group reported drug-related headache (38.0% versus 22.0%), flushing (14.5% versus 6.0%), erection increased (6.3% of males versus 0.8% of males), spontaneous penile erection (6.3% of males versus 0.8% of males), and epistaxis (7.5% versus 1.5%).

Common drug-related TEAEs (reported by $\geq 2\%$ of all subjects) are summarized in [Table 26](#). TEAEs considered not related to study drug by the Investigator are summarized in [Table 14.3.7B](#).

Table 26: Most Common (≥2% of All Subjects) Treatment-emergent Adverse Events Related to Study Drug (Safety Population)

System Organ Class Preferred Term:	Udenafil (N=200) n (%)	Placebo (N=200) n (%)
Subjects with ≥1 TEAE related to study drug	132 (66.0)	85 (42.5)
Gastrointestinal disorders	30 (15.0)	19 (9.5)
Abdominal pain upper	6 (3.0)	6 (3.0)
Nausea	13 (6.5)	7 (3.5)
General disorders and administration site conditions	19 (9.5)	15 (7.5)
Chest pain	3 (1.5)	6 (3.0)
Fatigue	5 (2.5)	7 (3.5)
Infections and infestations	14 (7.0)	7 (3.5)
Upper respiratory tract infection	7 (3.5)	3 (1.5)
Nervous system disorders	89 (44.5)	55 (27.5)
Dizziness	13 (6.5)	14 (7.0)
Headache	76 (38.0)	44 (22.0)
Migraine	5 (2.5)	4 (2.0)
Reproductive system and breast disorders	15 (7.5)	3 (1.5)
Erection increased ^a	7 (6.3)	1 (0.8)
Spontaneous penile erection ^a	7 (6.3)	1 (0.8)
Respiratory, thoracic and mediastinal disorders	27 (13.5)	13 (6.5)
Epistaxis	15 (7.5)	3 (1.5)
Nasal congestion	5 (2.5)	4 (2.0)
Vascular disorders	31 (15.5)	13 (6.5)
Flushing	29 (14.5)	12 (6.0)

TEAE=treatment-emergent adverse event

a Percentage calculated based on number of male subjects in each treatment group.

Source: [Table 14.3.7A](#)

Program: [14_3_ae_tables.sas](#)

12.2.3 Analysis of Adverse Events

In this section, the most common TEAEs (reported by $\geq 5\%$ of all subjects) are summarized for subgroups defined by gender (female, male), race (Caucasian/White, non-Caucasian/White), ethnicity (Hispanic or Latino/Latina, not Hispanic or Latino/Latina), age (tertiles at baseline), and weight (tertiles at baseline). A notable difference between groups is defined as ≥ 5 percentage points.

Gender

In the udenafil group, there was a notable increase among females versus males for chest pain (7.9% versus 2.7%). The incidence of common TEAEs is summarized separately for females and males in [Table 27](#).

Among females (N=161), a notably greater percentage of subjects in the udenafil group experienced headache (40.4% udenafil, 26.4% placebo) and flushing (16.9% udenafil, 9.7% placebo). A notably greater percentage of subjects in the placebo group experienced dizziness (7.9% udenafil, 13.9% placebo).

Among males (N=239), a notably greater percentage of subjects in the udenafil group experienced nausea (10.8% udenafil, 2.3% placebo), vomiting (9.0% udenafil, 3.1% placebo), nasopharyngitis (11.7% udenafil, 6.3% placebo), headache (37.8% udenafil, 25.0% placebo), epistaxis (9.9% udenafil, 0.8% placebo), and flushing (12.6% udenafil, 3.9% placebo). A notably greater percentage of subjects in the placebo group experienced chest pain (2.7% udenafil, 10.2% placebo). In addition, the incidence of erection increased was greater in the udenafil group (6.3% udenafil, 0.8% placebo; [Table 14.3.5](#)).

Race

In the udenafil group, there was a notable increase among Caucasians/Whites versus non-Caucasians/Whites for dizziness (9.5% versus 3.4%). There was a notable decrease among Caucasians/Whites versus non-Caucasians/Whites for nausea (8.3% versus 13.8%), nasopharyngitis (8.9% versus 17.2%), and headache (37.9% versus 44.8%). Given the disparity in sample sizes between the racial groups, these differences are difficult to interpret. The incidence of common TEAEs is summarized separately for Caucasians/Whites and non-Caucasians/Whites in [Table 28](#).

Among Caucasians/Whites (N=324), a notably greater percentage of subjects in the udenafil group experienced headache (37.9% udenafil, 27.1% placebo), epistaxis (9.5% udenafil, 3.2% placebo), and flushing (14.8% udenafil, 7.1% placebo).

Among non-Caucasians/Whites (N=65), a notably greater percentage of subjects in the udenafil group experienced nausea (13.8% udenafil, 5.6% placebo), vomiting (10.3% udenafil, 0 placebo), nasopharyngitis (17.2% udenafil, 8.3% placebo), headache (44.8% udenafil, 16.7% placebo), epistaxis (13.8% udenafil, 2.8% placebo), and flushing (13.8% udenafil, 2.8% placebo).

Ethnicity

In the udenafil group, there was a notable increase among Hispanic or Latino/Latina subjects versus subjects not Hispanic or Latino/Latina for vomiting (12.9% versus 6.5%). There was a notable increase among subjects not Hispanic or Latino/Latina versus Hispanic or Latino/Latina subjects for upper respiratory tract infection (8.3% versus 0) and flushing (15.5% versus 9.7%). Given the disparity in sample sizes between the ethnic groups, these differences are difficult to interpret. The incidence of common TEAEs is summarized separately for Hispanic or Latino/Latina subjects and subjects not Hispanic or Latino/Latina in [Table 29](#).

Among Hispanic or Latino/Latina subjects (N=56), a notably greater percentage of subjects in the udenafil group experienced nausea (12.9% udenafil, 4.0% placebo), nasopharyngitis (9.7% udenafil, 0 placebo), headache (41.9% udenafil, 28.0% placebo) and epistaxis (9.7% udenafil, 0 placebo). A notably greater percentage of subjects in the placebo group experienced chest pain (3.2% udenafil, 24.0% placebo).

Among subjects not Hispanic or Latino/Latina (N=342), a notably greater percentage of subjects in the udenafil group experienced headache (38.1% udenafil, 25.3% placebo), epistaxis (10.1% udenafil, 3.4% placebo), and flushing (15.5% udenafil, 5.7% placebo).

Age at Baseline

For age at baseline, comparisons are focused on the extremes of the age range (ie, low tertile versus high tertile). In the udenafil group, there was a notable increase among subjects within the high age tertile versus subjects in the low age tertile for nasopharyngitis (15.2% versus 8.3%). There was a notable increase among subjects in the low age tertile versus subjects in the high age tertile for flushing (18.1% versus 12.1%). The incidence of common TEAEs is summarized separately for baseline age tertiles in [Table 30](#).

Within the low age tertile (N=133), a notably greater percentage of subjects in the udenafil group experienced dizziness (11.1% udenafil, 4.9% placebo), headache (38.9% udenafil,

29.5% placebo), epistaxis (12.5% udenafil, 4.9% placebo), and flushing (18.1% udenafil, 1.6% placebo).

Within the high age tertile (N=133), a notably greater percentage of subjects in the udenafil group experienced nausea (9.1% udenafil, 0 placebo), vomiting (10.6% udenafil, 1.5% placebo), nasopharyngitis (15.2% udenafil, 0 placebo), headache (36.4% udenafil, 25.4% placebo), and flushing (12.1% udenafil, 6.0% placebo). A notably greater percentage of subjects in the placebo group experienced chest pain (6.1% udenafil, 11.9% placebo) and upper respiratory tract infection (6.1% udenafil, 11.9% placebo).

Among males in the high age tertile, a greater percentage of subjects in the udenafil group than the placebo group reported erection increased and spontaneous penile erection (7.9% versus 0 for each event; [Table 14.3.9C](#)).

Weight at Baseline

For weight at baseline, comparisons are focused on the extremes of the weight range (ie, low tertile versus high tertile). In the udenafil group, there was a notable increase in the low weight tertile versus the high weight tertile for the percentage of subjects experiencing nausea (9.3% versus 3.5%), headache (41.3% versus 28.1%), and flushing (16.0% versus 10.5%). The incidence of common TEAEs is summarized separately for baseline weight tertiles in [Table 31](#).

Within the low weight tertile (N=134), a notably greater percentage of subjects in the udenafil group experienced headache (41.3% udenafil, 23.7% placebo), epistaxis (13.3% udenafil, 3.4% placebo), and flushing (16.0% udenafil, 1.7% placebo). A notably greater percentage of subjects in the placebo group experienced chest pain (2.7% udenafil, 8.5% placebo) and dizziness (6.7% udenafil, 11.9% placebo).

Within the high weight tertile (N=134), a notably greater percentage of subjects in the udenafil group experienced vomiting (8.8% udenafil, 2.6% placebo). A notably greater percentage of subjects in the placebo group experienced chest pain (1.8% udenafil, 7.8% placebo).

Among male subjects, a greater percentage of subjects in the udenafil group than the placebo group reported erection increased and spontaneous penile erection in the low weight tertile (5.0% versus 0 and 10.0% versus 3.0%, respectively; [Table 14.3.8A](#)) and in the high weight tertile (5.6% versus 0 and 8.3% versus 0, respectively; [Table 14.3.8C](#)).

Table 27: Most Common (≥5% of All Subjects) Treatment-emergent Adverse Events by Gender (Safety Population)

Preferred Term:	Male Subjects (N=239)			Female Subjects (N=161)		
	Udenafil (N=111) n (%)	Placebo (N=128) n (%)	Total (N=239) n (%)	Udenafil (N=89) n (%)	Placebo (N=72) n (%)	Total (N=161) n (%)
Nausea	12 (10.8)	3 (2.3)	15 (6.3)	7 (7.9)	6 (8.3)	13 (8.1)
Vomiting	10 (9.0)	4 (3.1)	14 (5.9)	5 (5.6)	2 (2.8)	7 (4.3)
Chest pain	3 (2.7)	13 (10.2)	16 (6.7)	7 (7.9)	5 (6.9)	12 (7.5)
Nasopharyngitis	13 (11.7)	8 (6.3)	21 (8.8)	7 (7.9)	5 (6.9)	12 (7.5)
Upper respiratory tract infection	7 (6.3)	8 (6.3)	15 (6.3)	7 (7.9)	9 (12.5)	16 (9.9)
Dizziness	10 (9.0)	8 (6.3)	18 (7.5)	7 (7.9)	10 (13.9)	17 (10.6)
Headache	42 (37.8)	32 (25.0)	74 (31.0)	36 (40.4)	19 (26.4)	55 (34.2)
Epistaxis	11 (9.9)	1 (0.8)	12 (5.0)	9 (10.1)	5 (6.9)	14 (8.7)
Flushing	14 (12.6)	5 (3.9)	19 (7.9)	15 (16.9)	7 (9.7)	22 (13.7)

Source: [Table 14.3.4A](#) and [Table 14.3.4B](#)

Program: [14_3_ae_tables.sas](#)

Table 28: Most Common (≥5% of All Subjects) Treatment-emergent Adverse Events by Race Category (Safety Population)

Preferred Term:	Caucasian/White Subjects (N=324)			Non-Caucasian/White Subjects (N=65)		
	Udenafil (N=169) n (%)	Placebo (N=155) n (%)	Total (N=324) n (%)	Udenafil (N=29) n (%)	Placebo (N=36) n (%)	Total (N=65) n (%)
Nausea	14 (8.3)	6 (3.9)	20 (6.2)	4 (13.8)	2 (5.6)	6 (9.2)
Vomiting	11 (6.5)	4 (2.6)	15 (4.6)	3 (10.3)	0	3 (4.6)
Chest pain	8 (4.7)	14 (9.0)	22 (6.8)	2 (6.9)	2 (5.6)	4 (6.2)
Nasopharyngitis	15 (8.9)	10 (6.5)	25 (7.7)	5 (17.2)	3 (8.3)	8 (12.3)
Upper respiratory tract infection	13 (7.7)	17 (11.0)	30 (9.3)	1 (3.4)	0	1 (1.5)
Dizziness	16 (9.5)	12 (7.7)	28 (8.6)	1 (3.4)	3 (8.3)	4 (6.2)
Headache	64 (37.9)	42 (27.1)	106 (32.7)	13 (44.8)	6 (16.7)	19 (29.2)
Epistaxis	16 (9.5)	5 (3.2)	21 (6.5)	4 (13.8)	1 (2.8)	5 (7.7)
Flushing	25 (14.8)	11 (7.1)	36 (11.1)	4 (13.8)	1 (2.8)	5 (7.7)

Note: Summary excludes 11 subjects of unknown or not reported race.

Source: [Table 14.3.4C](#) and [Table 14.3.4D](#)

Program: [14_3_ae_tables.sas](#)

Table 29: Most Common (≥5% of All Subjects) Treatment-emergent Adverse Events by Ethnicity Category (Safety Population)

Preferred Term:	Hispanic or Latino/Latina Subjects (N=56)			Not Hispanic or Latino/Latina Subjects (N=342)		
	Udenafil (N=31) n (%)	Placebo (N=25) n (%)	Total (N=56) n (%)	Udenafil (N=168) n (%)	Placebo (N=174) n (%)	Total (N=342) n (%)
Nausea	4 (12.9)	1 (4.0)	5 (8.9)	15 (8.9)	8 (4.6)	23 (6.7)
Vomiting	4 (12.9)	3 (12.0)	7 (12.5)	11 (6.5)	3 (1.7)	14 (4.1)
Chest pain	1 (3.2)	6 (24.0)	7 (12.5)	9 (5.4)	12 (6.9)	21 (6.1)
Nasopharyngitis	3 (9.7)	0	3 (5.4)	17 (10.1)	13 (7.5)	30 (8.8)
Upper respiratory tract infection	0	0	0	14 (8.3)	17 (9.8)	31 (9.1)
Dizziness	2 (6.5)	2 (8.0)	4 (7.1)	15 (8.9)	16 (9.2)	31 (9.1)
Headache	13 (41.9)	7 (28.0)	20 (35.7)	64 (38.1)	44 (25.3)	108 (31.6)
Epistaxis	3 (9.7)	0	3 (5.4)	17 (10.1)	6 (3.4)	23 (6.7)
Flushing	3 (9.7)	2 (8.0)	5 (8.9)	26 (15.5)	10 (5.7)	36 (10.5)

Note: Summary excludes 2 subjects of unknown ethnicity.

Source: [Table 14.3.4E](#) and [Table 14.3.4F](#)

Program: [14_3_ae_tables.sas](#)

Table 30: Most Common (≥5% of All Subjects) Treatment-emergent Adverse Events by Baseline Age Tertile (Safety Population)

Preferred Term:	Low Age Tertile (N=133)			Medium Age Tertile (N=134)			High Age Tertile (N=133)		
	Udenafil (N=72) n (%)	Placebo (N=61) n (%)	Total (N=133) n (%)	Udenafil (N=62) n (%)	Placebo (N=72) n (%)	Total (N=134) n (%)	Udenafil (N=66) n (%)	Placebo (N=67) n (%)	Total (N=133) n (%)
Nausea	9 (12.5)	5 (8.2)	14 (10.5)	4 (6.5)	4 (5.6)	8 (6.0)	6 (9.1)	0	6 (4.5)
Vomiting	6 (8.3)	3 (4.9)	9 (6.8)	2 (3.2)	2 (2.8)	4 (3.0)	7 (10.6)	1 (1.5)	8 (6.0)
Chest pain	3 (4.2)	2 (3.3)	5 (3.8)	3 (4.8)	8 (11.1)	11 (8.2)	4 (6.1)	8 (11.9)	12 (9.0)
Nasopharyngitis	6 (8.3)	7 (11.5)	13 (9.8)	4 (6.5)	6 (8.3)	10 (7.5)	10 (15.2)	0	10 (7.5)
Upper respiratory tract infection	7 (9.7)	6 (9.8)	13 (9.8)	3 (4.8)	3 (4.2)	6 (4.5)	4 (6.1)	8 (11.9)	12 (9.0)
Dizziness	8 (11.1)	3 (4.9)	11 (8.3)	3 (4.8)	8 (11.1)	11 (8.2)	6 (9.1)	7 (10.4)	13 (9.8)
Headache	28 (38.9)	18 (29.5)	46 (34.6)	26 (41.9)	16 (22.2)	42 (31.3)	24 (36.4)	17 (25.4)	41 (30.8)
Epistaxis	9 (12.5)	3 (4.9)	12 (9.0)	6 (9.7)	1 (1.4)	7 (5.2)	5 (7.6)	2 (3.0)	7 (5.3)
Flushing	13 (18.1)	1 (1.6)	14 (10.5)	8 (12.9)	7 (9.7)	15 (11.2)	8 (12.1)	4 (6.0)	12 (9.0)

Source: [Table 14.3.9A](#), [Table 14.3.9B](#), and [Table 14.3.9C](#)

Program: [14_3_ae_tables.sas](#)

Table 31: Most Common (≥5% of All Subjects) Treatment-emergent Adverse Events by Baseline Weight Tertile (Safety Population)

Preferred Term:	Low Weight Tertile (N=134)			Medium Weight Tertile (N=132)			High Weight Tertile (N=134)		
	Udenafil (N=75) n (%)	Placebo (N=59) n (%)	Total (N=134) n (%)	Udenafil (N=68) n (%)	Placebo (N=64) n (%)	Total (N=132) n (%)	Udenafil (N=57) n (%)	Placebo (N=77) n (%)	Total (N=134) n (%)
Nausea	7 (9.3)	4 (6.8)	11 (8.2)	10 (14.7)	1 (1.6)	11 (8.3)	2 (3.5)	4 (5.2)	6 (4.5)
Vomiting	6 (8.0)	2 (3.4)	8 (6.0)	4 (5.9)	2 (3.1)	6 (4.5)	5 (8.8)	2 (2.6)	7 (5.2)
Chest pain	2 (2.7)	5 (8.5)	7 (5.2)	7 (10.3)	7 (10.9)	14 (10.6)	1 (1.8)	6 (7.8)	7 (5.2)
Nasopharyngitis	5 (6.7)	5 (8.5)	10 (7.5)	11 (16.2)	4 (6.3)	15 (11.4)	4 (7.0)	4 (5.2)	8 (6.0)
Upper respiratory tract infection	7 (9.3)	7 (11.9)	14 (10.4)	3 (4.4)	4 (6.3)	7 (5.3)	4 (7.0)	6 (7.8)	10 (7.5)
Dizziness	5 (6.7)	7 (11.9)	12 (9.0)	6 (8.8)	4 (6.3)	10 (7.6)	6 (10.5)	7 (9.1)	13 (9.7)
Headache	31 (41.3)	14 (23.7)	45 (33.6)	31 (45.6)	16 (25.0)	47 (35.6)	16 (28.1)	21 (27.3)	37 (27.6)
Epistaxis	10 (13.3)	2 (3.4)	12 (9.0)	5 (7.4)	0	5 (3.8)	5 (8.8)	4 (5.2)	9 (6.7)
Flushing	12 (16.0)	1 (1.7)	13 (9.7)	11 (16.2)	4 (6.3)	15 (11.4)	6 (10.5)	7 (9.1)	13 (9.7)

Source: [Table 14.3.8A](#), [Table 14.3.8B](#), and [Table 14.3.8C](#)

Program: [14_3_ae_tables.sas](#)

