12.2.2 Display of Adverse Events

TEAEs reported by $\geq 5\%$ of subjects in the udenafil group ([Table 14.3.5](#)) included headache (39.0%), flushing (14.5%), epistaxis (10.0%), nasopharyngitis (10.0%), nausea (9.5%), dizziness (8.5%), vomiting (7.5%), upper respiratory tract infection (7.0%), erection increased (6.3% of males), spontaneous penile erection (6.3% of males), influenza (5.5%), chest pain (5.0%), pharyngitis streptococcal (5.0%), and rash (5.0%). TEAEs reported by $\geq 5\%$ of subjects in the placebo group included headache (25.5%), chest pain (9.0%), dizziness (9.0%), upper respiratory tract infection (8.5%), nasopharyngitis (6.5%), flushing (6.0%), and fatigue (5.5%).

A notably greater percentage (≥ 5 percentage points) of subjects in the udenafil group as compared to the placebo group reported headache (39.0% versus 25.5%), flushing (14.5% versus 6.0%), epistaxis (10.0% versus 3.0%), nausea (9.5% versus 4.5%), and erection increased (6.3% of males versus 0.8% of males) ([Table 14.3.5](#)).

Common TEAEs (reported by $\geq 5\%$ of all subjects) are summarized in [Table 25](#).

Table 25: Most Common (≥5% of All Subjects) Treatment-emergent Adverse Events (Safety Population)

System Organ Class Preferred Term:	Udenafil (N=200) n (%)	Placebo (N=200) n (%)
Subjects with ≥1 TEAE	158 (79.0)	135 (67.5)
Gastrointestinal disorders	55 (27.5)	33 (16.5)
Nausea	19 (9.5)	9 (4.5)
Vomiting	15 (7.5)	6 (3.0)
General disorders and administration site conditions	33 (16.5)	39 (19.5)
Chest pain	10 (5.0)	18 (9.0)
Infections and infestations	69 (34.5)	60 (30.0)
Nasopharyngitis	20 (10.0)	13 (6.5)
Upper respiratory tract infection	14 (7.0)	17 (8.5)
Nervous system disorders	95 (47.5)	65 (32.5)
Dizziness	17 (8.5)	18 (9.0)
Headache	78 (39.0)	51 (25.5)
Respiratory, thoracic and mediastinal disorders	45 (22.5)	29 (14.5)
Epistaxis	20 (10.0)	6 (3.0)
Vascular disorders	32 (16.0)	14 (7.0)
Flushing	29 (14.5)	12 (6.0)

TEAE=treatment-emergent adverse event

Source: [Table 14.3.3](#) and [Table 14.3.5](#)Program: [14_3_ae_tables.sas](#)

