12.6 Safety Conclusions

A notably larger percentage (≥ 5 percentage points) of udenafil-treated than placebo-treated subjects reported at least 1 TEAE (79.0% versus 67.5%) and at least 1 drug-related TEAE (66.0% versus 42.5%). The incidence of TEAEs of Grade ≥ 3 , serious TEAEs, drug-related serious TEAEs, and TEAEs resulting in temporary or permanent discontinuation of study drug was similar between treatment groups.

A notably greater percentage (≥ 5 percentage points) of subjects in the udenafil group as compared to the placebo group reported headache (39.0% versus 25.5%), flushing (14.5% versus 6.0%), epistaxis (10.0% versus 3.0%), nausea (9.5% versus 4.5%), and erection increased (6.3% of males versus 0.8% of males).

There were no clinically important differences in the TEAE profile among subgroups defined by gender (female, male), race (Caucasian/White, non-Caucasian/White), ethnicity (Hispanic or Latino/Latina, not Hispanic or Latino/Latina), age (tertiles at baseline), and weight (tertiles at baseline).

Severe TEAEs were reported for 10 (5.0%) udenafil-treated subjects and 6 (3.0%) placebo-treated subjects; no life-threatening TEAEs were reported in either treatment group. Dizziness was the only severe TEAE reported by > 1 subject (2 placebo subjects).

No subject died during the study. At least 1 serious TEAE was reported by 14 (7.0%) subjects in the udenafil group and 10 (5.0%) subjects in the placebo group. No individual serious TEAE was reported by > 2 subjects in either treatment group. Hospitalization was reported for 23 subjects (14 udenafil, 9 placebo) during the study. No transplants were reported.

At least 1 TEAE leading to temporary or permanent discontinuation of study drug was reported by 18 (9.0%) subjects in the udenafil group and 13 (6.5%) subjects in the placebo group. Headache was the only TEAE leading to temporary or permanent discontinuation of study drug reported by > 2 subjects in either treatment group (3 subjects each in the udenafil and placebo groups).

There were no clinically important treatment group differences for clinical laboratory findings and vital signs.

Overall, udenafil was safe and well tolerated in this study.

13 Discussion and Overall Conclusions

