6.5 Safety Evaluations

Safety assessments will be summarized for the Safety Population. No formal hypothesis testing will be performed.

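### The fixed 5-point rule for a notable adverse-event difference ignores subgroup size, and its comparisons within the udenafil arm cannot show that a subgroup modifies the drug's effect

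*Protocol*

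**What the plan says.** Protocol section 12.2.3 reviews the TEAEs reported by at least 5% of all subjects (nine preferred terms in Table 25) by gender, race, ethnicity, age tertile and weight tertile. The threshold is stated once: "A notable difference between groups is defined as" 5 percentage points or more. It is then used in two ways:

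- **Between arms:** udenafil against placebo inside each subgroup.
- **Within udenafil:** one subgroup against another, using udenafil subjects only. For example: "In the udenafil group, there was a notable increase among females versus males for chest pain (7.9% versus 2.7"; and "In the udenafil group, there was a notable increase among Hispanic or Latino/Latina subjects versus subjects not Hispanic or Latino/Latina for vomiting (12.9% versus 6.5".

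For age and weight the text compares only the low and high tertiles; the medium tertiles appear in Tables 30 and 31. After the within-udenafil comparisons for race and for ethnicity, the text says that unequal group sizes make the differences hard to interpret. It says nothing similar for gender, age or weight.

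Section 12.6 concludes: "There were no clinically important differences in the TEAE profile among subgroups defined by gender (female, male" and likewise for race, ethnicity, age and weight. Section 13 repeats this.

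SAP section 6.5 keeps safety descriptive: "No formal hypothesis testing will be performed". SAP 6.5.2 plans TEAE summaries by age and weight tertile and contains no 5-point rule. Protocol 9.8.2.1 records that the gender, race and ethnicity summaries were added.

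**The concern.** The only input to the rule is the raw gap between two percentages. In an arm of 25 subjects, 5 points is 1.25 subjects (25 × 0.05); in an arm of 75 it is 3.75. Gaps of that size arise readily by chance, so the same word carries very different evidence in adjacent paragraphs.

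The within-udenafil use has a second problem. A subgroup can have a higher event rate on udenafil because its background rate is higher. Without the placebo rate, the comparison says nothing about whether the drug acts differently there.

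At stake is the subgroup safety conclusion. A reader is given a list of flags of very uneven reliability and then a single negative statement that they neither support nor refute.

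**Working it through.** **Inputs.** Subgroup sizes and counts come from Protocol Tables 27 to 31, overall counts from Table 25. Pooled rates over 400 subjects run from 21/400 = 5.25% (vomiting) to 129/400 = 32.25% (headache). Udenafil rates are the Table 25 counts over 200.

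**Step 1: reproduce the text.** Applying the 5-point rule to the tabulated counts returns exactly the flags listed for the nine TEAEs:

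- Within udenafil: gender 1 + race 4 + ethnicity 3 + age 2 + weight 3 = 13, out of 5 × 9 = 45 comparisons.
- Between arms, in the ten subgroups discussed: 45, out of 10 × 9 = 90 comparisons.

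**Step 2: between-arm flags with no true difference.** For each TEAE with pooled rate p, the flag probability is P(|x1/n1 − x2/n2| ≥ 0.05), with x1 and x2 independent binomials of sizes n1 and n2 and common rate p, by exact enumeration. The expected count is the sum over nine TEAEs. The chance of at least one flag is 1 − ∏(1 − flag probability).

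| Subgroup | n udenafil / placebo | Expected flags of 9 | P(at least one) | Flags listed |
|---|---|---|---|---|
| Not Hispanic | 168 / 174 | 0.95 | 0.65 | 3 |
| White | 169 / 155 | 1.04 | 0.68 | 3 |
| Male | 111 / 128 | 1.54 | 0.83 | 7 |
| Female | 89 / 72 | 2.31 | 0.94 | 3 |
| High age | 66 / 67 | 2.50 | 0.95 | 7 |
| Low weight | 75 / 59 | 2.66 | 0.96 | 5 |
| High weight | 57 / 77 | 2.72 | 0.96 | 2 |
| Low age | 72 / 61 | 2.75 | 0.97 | 4 |
| Non-White | 29 / 36 | 3.85 | 0.99 | 6 |
| Hispanic | 31 / 25 | 4.40 | 0.998 | 5 |
| All ten | | 24.7 of 90 | | 45 |

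The average flag rate per TEAE is therefore 0.95/9, about 11%, in not-Hispanic subjects and 4.40/9 = 49% in Hispanic subjects. Over all 90 comparisons it is 24.7/90 = 27%.

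Of the 45 observed flags, 37 are higher on udenafil and 19 have Fisher p < 0.05. Headache is flagged in nine of the ten subgroups, in line with the overall 39.0% versus 25.5%.

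**Step 3: within-udenafil flags with no true difference.** The formula is the same, with the overall udenafil rates and sizes 89 v 111, 169 v 29, 31 v 168, 66 v 72 and 75 v 57. Expected flags are 2.12 + 3.57 + 3.50 + 2.99 + 2.98 = 15.2 of 45, or 34% per comparison. The SD is about 3.1 and the central 95% range about 9 to 22. The text lists 13, and P(13 or fewer) is 0.24 to 0.33 depending on the method. The smallest Fisher p among all 45 comparisons is 0.11.

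**Step 4: what leaving out placebo does.** Chest pain is flagged as higher in udenafil females than in udenafil males. From Table 27:

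- Females: 7.9 − 6.9 = +1.0 point (7/89 − 5/72 gives +0.9 from the counts).
- Males: 2.7 − 10.2 = −7.5 points (3/111 − 13/128).

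The flag reflects a low rate in udenafil males, not an excess over placebo in females. The contrast of the two differences from the counts is 8.4 points, Wald 95% CI −1.7 to 18.5.

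The layout also leaves things out:

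- **Chest pain by ethnicity** is not flagged within udenafil (3.2% v 5.4%). The differences from placebo are −20.8 points in Hispanic and −1.5 in not-Hispanic subjects, a contrast of 19.2 points in size (CI 0.7 to 37.8).
- **Nausea in the medium weight tertile** is 14.7% v 1.6%, a difference of +13.1 points (CI 4.2 to 22.1). The text does not mention it, because it compares only low with high.

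These intervals are unadjusted, and the contrasts may themselves be chance.

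**Robustness.** Allowing the nine TEAEs to be correlated within subjects (latent correlation up to 0.5) leaves the lowest chance of at least one flag at 0.61 and the expected within-udenafil count at about 15.2.

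**The case against.** The strongest reply is that the rule does carry information in its main use. Between arms there are 45 flags against 24.7 expected, mostly in the direction of udenafil. That stands. A reader might infer from the chance rates that the rule cannot separate signal from noise at all; the documents do not support this. It holds for the within-udenafil flags only. A reader might also make something of 13 being below 15.2, but that is 0.7 SD and is not a real deficit.

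Second, the text itself says that the within-udenafil race and ethnicity differences are hard to interpret, and those two factors hold 7 of the 13 flags. This also stands. It leaves the 6 flags for gender, age and weight without a caveat, and the caveat does not reach sections 12.6 and 13.

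Third, notable is a descriptive label and clinical importance is a judgement, so listing gaps and then judging none important is not a contradiction. That is right, and no contradiction is claimed. No subgroup claim is built on a flag either. The difficulty is that differences described as uninterpretable do not support a conclusion that none matters.

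Fourth, safety was planned as descriptive, every count is printed, and many unadjusted intervals bring their own chance findings. All true. An interval is still descriptive, and unlike a fixed threshold it shows how little a small subgroup can say.

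**Conclusion.** The point holds in limited form. The 5-point rule takes no account of precision, so its chance flag rate varies more than fourfold across subgroups (about 11% to 49% per TEAE). The within-udenafil flags are no more than chance predicts and, without placebo, cannot show effect modification. The between-arm flags as a set exceed chance, although single flags in small subgroups are weak evidence. The uniform negative statement in sections 12.6 and 13 is firmer than these data allow.

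None of this shows that a real subgroup difference exists or was missed.

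Assumptions: a common event rate within each comparison, and independence of TEAEs for the chance of at least one flag (the expected counts do not need it). At placebo rather than pooled rates, the expected between-arm count falls to 20.7. The ten subgroups overlap, so no p-value is attached to 45 against 24.7. The point is minor: it concerns the subgroup safety text, not the efficacy or overall safety results.

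**What to change.** 1. In section 12.2.3, replace the 5-point definition with the udenafil-minus-placebo risk difference and its 95% CI for the nine common TEAEs in all 12 subgroups, including the medium tertiles.
2. For each factor, add a between-subgroup contrast of those differences with its CI. For the tertile factors, state which contrast is used.
3. Label all of this descriptive and unadjusted for multiplicity. With 9 × 12 = 108 intervals, about 108 × 0.05 = 5 would exclude zero by chance at nominal coverage, and the text should say so.
4. Delete the within-udenafil statements of notable increase or decrease for all five factors, including weight.
5. Reword sections 12.6 and 13 to say that the subgroup data are too imprecise to show or exclude differences, citing the intervals. The Synopsis, which describes the extension study, already takes a similar line for race and ethnicity.

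The cost is one re-run of tables whose counts already exist, and a weaker concluding statement. No hypothesis test is added, so the SAP's descriptive approach to safety is kept.
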